## **10.9 Biohazard containment**

As the transmission of HIV and other blood-borne pathogens can occur through contact with contaminated needles, blood, and blood products, appropriate precautions will be employed by all personnel in the drawing of blood and shipping and handling of all specimens for this study, as currently recommended by the CDC and the NIH or other applicable agencies.

All dangerous goods materials, including Biological Substances, Category A or Category B, must be transported according to instructions detailed in the International Air Transport Association Dangerous Goods Regulations.

## **11 Safety monitoring and safety review**

### **11.1 Safety monitoring and oversight**

#### **11.1.1 HVTN 128 PSRT**

The HVTN 128 PSRT is composed of the following members:

- DAIDS medical officer representative
- Protocol chair and co-chair
- Protocol Team leader
- Core medical monitor
- Clinical safety specialist

The clinician members of the HVTN 128 PSRT are responsible for decisions related to participant safety.

The Protocol Team clinic coordinator, clinical data manager, study product developer representative, clinical trial manager, and others may also be included in HVTN 128 PSRT meetings.

#### **11.1.2 HVTN SMB**

The SMB is a multidisciplinary group consisting of biostatisticians, clinicians, and experts in HIV prevention and drug research that, collectively, has experience in the conduct and monitoring of prevention and drug trials. Members of the SMB are not directly affiliated with the protocols under review.

The SMB reviews safety data, unblinded as to treatment arm, approximately every 4 months. The reviews consist of evaluation of cumulative Solicited AEs, Unsolicited AEs, laboratory safety data, and individual reports of AEs requiring expedited reporting to DAIDS. The SMB conducts additional special reviews at the request of the HVTN 128 PSRT.

Study sites will receive SMB summary minutes and are responsible for forwarding them to their IRB/EC and any applicable RE.

#### **11.1.3 SDMC roles and responsibilities in safety monitoring**

The roles and responsibilities of the SDMC in relation to safety monitoring include:

- Maintaining a central database management system for clinical data;

- Providing reports of clinical data to appropriate groups such as the HVTN 128 PSRT and HVTN SMB (see Section 11.1.2);

#### **11.1.4 HVTN Core roles and responsibilities in safety monitoring**

The roles and responsibilities of the HVTN CSS or HVTN Core designee in relation to safety monitoring include:

- Daily monitoring of clinical data for events that meet the safety pause and HVTN 128 PSRT AE review criteria (see Section 11.3);
- Notifying HVTN CRSs and other groups when safety pauses or planned holds are instituted and lifted (see Section 11.3);
- Querying HVTN CRSs for additional information regarding reported clinical data; and
- Providing support to the HVTN 128 PSRT.

### **11.2 Safety reporting**

#### **11.2.1 Submission of safety forms to SDMC**

Site staff must submit all safety forms (eg, Solicited AEs, Unsolicited AEs, urinalysis, local lab results, and concomitant medications) before the end of the next business day, excluding federal or bank holidays. The forms should not be held in anticipation of additional information at a later date. If additional information is received at a later date, the forms should be updated and resubmitted before the end of the next business day after receiving the new information. For the case of a longer site holiday closure, site staff must submit the data by the end of the 5th day (local time) after receiving the information even if this day is a holiday.

For example: If the site becomes aware of an AE on Thursday (Day 0), the site must submit the data by the end of the next business day, on Friday. If there is a longer site holiday closure, then this AE must be reported no later than the end of the fifth day, Monday (Day 4). If Monday is a holiday as well, all safety forms still need to be submitted by the end of Monday (Day 4).

#### **11.2.2 AE reporting**

An AE is any untoward medical occurrence in a clinical investigation participant administered a study product/procedure(s) and which does not necessarily have a causal relationship with this treatment. An AE can therefore be any unfavorable and unintended sign (including an abnormal laboratory finding), symptom, or disease temporally associated with the use of an investigational study product/procedure(s), whether or not related to the investigational study

product/procedure(s). See the Ab MOP and SSP for further detail regarding Solicited and Unsolicited AEs.

The study Unsolicited AE reporting period is from study enrollment of a trial participant to completion of the safety contact two weeks after the last biopsy collection at Week 50.

All AEs are graded according to the Division of AIDS (DAIDS) Table for Grading the Severity of Adult and Pediatric Adverse Events, Corrected Version 2.1, July 2017, available on the RSC website at <http://rsc.tech-res.com/clinical-research-sites/safety-reporting/daids-grading-tables>, except:

- Unintentional Weight Loss is required to be reported as an AE only if it is considered to be potentially deleterious to the participant's health (see HVTN 128 SSP);
- Infusion Site Erythema or Redness and Infusion Site Induration or Swelling will not consider interference with usual social and functional activities such that:
  - Grade 1 is: 2.5 to < 5 cm in diameter OR 6.25 to < 25 cm^2 surface area;
  - Grade 2 is: ≥ 5 to < 10 cm in diameter OR ≥ 25 to < 100 cm^2 surface area;
  - Grade 3 is: ≥ 10 cm in diameter OR ≥ 100 cm^2 surface area OR Ulceration OR Secondary infection OR Phlebitis OR Sterile abscess OR Drainage;
  - Grade 4 is: Potentially life-threatening consequences (eg, abscess, exfoliative dermatitis, necrosis involving dermis or deeper tissue);
- Monoclonal antibody reactions (see HVTN 128 SSP)

All AEs are reported to the SDMC on the appropriate CRF. Clinic staff should evaluate every AE to determine if (1) the AE meets the requirements for expedited reporting to DAIDS (see Section 11.2.3) and (2), and (3) if the AE is listed as an AESI. A list of AESI to be reported in this protocol is provided in [Appendix H](#).

Sites are expected to notify HVTN clinical safety staff of any serious safety concern requiring their attention ([Table 11-1](#)). Telephone numbers and email addresses are found on the protocol home page on the HVTN Members' site (<https://members.hvtn.org/protocols/hvtn128>). Concerns requiring immediate attention should be communicated by calling the clinical safety phone.

In the case of email notification, clinical safety staff will reply during working hours (their local time) to confirm that the email has been received and reviewed. If email service is not available, the HVTN CRS should notify clinical safety staff of the event by telephone, then submit CRFs.

In addition, site investigators are required to submit AE information in accordance with IRB/EC and any applicable RE requirements.

### **11.2.3 Expedited reporting of AEs to DAIDS**

Requirements, definitions and methods for expedited reporting of AEs are outlined in Version 2.0 (January 2010) of the *Manual for Expedited Reporting of Adverse Events to DAIDS* (DAIDS EAE Manual), which is available on the RSC website at <http://rsc.tech-res.com/clinical-research-sites/safety-reporting/manual>. The SAE Reporting Category will be used for this study.

The internet-based DAIDS Adverse Experience Reporting System (DAERS) must be used for expedited AE (EAE) reporting to DAIDS. In the event of system outages or technical difficulties, expedited AE reports may be submitted via the DAIDS EAE Form. This form is available on the DAIDS RSC website at <http://rsc.tech-res.com/clinical-research-sites/safety-reporting/daids/paper-eae-reporting>.

For questions about DAERS, please contact [[contact]](mailto:[contact]) or from within the DAERS application itself.

For questions about EAE reporting, please contact the DAIDS RSC Safety Office at ([[contact]](mailto:[contact])).

The study product for which expedited reporting are required is:

- VRC-HIVMAB075-00-AB (VRC07-523LS)

While the participant is in the study, from enrollment to the end of trial participation for that participant, the SAE Reporting Category will be used.

After the end of trial participation for that participant, unless otherwise noted, only Suspected, Unexpected Serious Adverse Reactions (SUSARs) as defined in Version 2.0 of the DAIDS EAE Manual must be reported to DAIDS, if the study staff become aware of the events. All AESI will be considered “unexpected”, and, if deemed related to the study products, will be reported as SUSARs, if applicable.

The NIAID/DAIDS will report all unexpected SAEs related to the study products observed in this clinical trial to the FDA in accordance with 21 CFR 312.32 (IND Safety Reports).

HVTN CRS Investigators of Record/designees will submit AE information and any other relevant safety information to their IRBs/ECs in accordance with IRB/EC requirements.

### 11.3 Safety pause and prompt PSRT AE review

When a trial is placed on safety pause, all enrollment and study product administration with the product related to the event that triggered the pause will be held until further notice. The AEs that will lead to a safety pause or prompt HVTN 128 PSRT AE review are summarized in [Table 11-1](#). Study product administrations may be suspended for safety concerns other than those described in the table, or before pause rules are met, if, in the judgment of the HVTN 128 PSRT, participant safety may be threatened. Criteria for an individual participant's departure from the schedule of study product administrations are listed in [Section 7.3](#).

**Table 11-1 AE notification and safety pause/AE review rules**

Event and relationship to study products	Severity	HVTN CRS action a	HVTN Core action b
SAE, related	Grade 5 or Grade 4	Phone immediately, email and submit forms immediately	Immediate pause
SAE, not related	Grade 5	Phone immediately, email and submit forms immediately	Immediate PSRT notification
SAE, related	Grade 3, 2, or 1	Email and submit forms immediately	Immediate PSRT notification and prompt PSRT AE review to consider pause
AE c , related	Grade 4 or 3	Email and submit forms immediately	Immediate PSRT notification and prompt PSRT AE review to consider pause

a Phone numbers and email addresses are found on the Protocol home page on the HVTN Members' site (<https://members.hvtn.org/protocols/hvtn128>).

b HVTN CSS or HVTN Core designee

c Does not include the following subjective Solicited AEs symptoms (infusion site pain and/or tenderness, fatigue/malaise, myalgia, arthralgia, chills, headache, non-exertional dyspnea, generalized pruritus, facial flushing, and unexplained diaphoresis).

For all safety pauses, HVTN Core notifies the HVTN 128 PSRT, HVTN Regulatory Affairs, DAIDS Pharmaceutical Affairs Branch (PAB), DAIDS Regulatory Affairs Branch (RAB), DAIDS Safety and Pharmacovigilance Team (SPT), and participating HVTN CRSs. When an immediate safety pause is triggered, HVTN Core notifies the SMB.

Once a trial is paused, the HVTN 128 PSRT reviews safety data and decides whether the pause can be lifted or permanent discontinuation of study product administration is appropriate, consulting the SMB if necessary. HVTN Core notifies the participating HVTN CRSs, HVTN Regulatory Affairs, DAIDS PAB, DAIDS RAB, and DAIDS SPT of the decision regarding resumption or discontinuation of study product administrations. Based on the HVTN 128 PSRT assessment, DAIDS RAB notifies the FDA as needed.

If an immediate HVTN 128 PSRT notification or prompt HVTN 128 PSRT AE review is triggered, HVTN Core notifies the HVTN 128 PSRT as soon as possible

during working hours (HVTN Core local time)—or, if the information was received during off hours, by the morning of the next workday. If a prompt HVTN 128 PSRT AE review cannot be completed within 72 hours of notification (excluding weekends and US federal holidays), an automatic safety pause occurs.

The HVTN requires that each HVTN CRS submit to its IRB/EC and any applicable RE protocol-related safety information (such as IND safety reports, notification of study-product holds due to the pause rules, unanticipated problems involving risks to participants or others, and notification of other unplanned safety pauses). HVTN CRSs must also follow all applicable RE reporting requirements.

In addition, all other AEs are reviewed routinely by the HVTN 128 PSRT (see Section [11.4.2](#)).

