### **2.5 Adequate safety monitoring**

#### **45 CFR 46.111 (a) 6 and 21 CFR 56.111 (a) 6: There is adequate provision for monitoring the data collected to ensure the safety of subjects.**

This protocol has extensive safety monitoring in place (see Section 9). Safety is monitored daily by HVTN clinical staff and routinely by the HVTN 128 Protocol Safety Review Team (PSRT). In addition, the HVTN Safety Monitoring Board (SMB) periodically reviews study data.

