### **7.3.3 Discontinuing study product administration for a participant**

Under certain circumstances, an individual participant's study product administrations will be permanently discontinued. Specific events that will result in stopping a participant's study product administration schedule include:

- Co-enrollment in a study with an investigational research agent (rare exceptions allowing for the continuation of study product administration may be granted with the unanimous consent of the HVTN 128 PSRT)
- Clinically significant condition (ie, a condition that affects the immune system or for which continued study product administration and/or blood draws may pose additional risk), including but not limited to the following:
  - HIV infection
  - Any grade 4 local or systemic Solicited or Unsolicited AE that is subsequently considered to be related to study product;

- Any grade 3 clinical AE (exception: fever and subjective local and systemic symptoms) that is subsequently considered to be related to study product (upon review, the HVTN 128 PSRT may allow continuation of study product administration if the participant has grade 3 erythema and/or induration)
  - Any grade 3 or 4 lab abnormality confirmed by a repeated value that is subsequently considered to be related to study product
  - SAE that is subsequently considered to be related to study product administration
  - Clinically significant hypersensitivity or mAb reaction including but not limited to type 1 hypersensitivity reaction, urticaria, or serum sickness associated with study product. Consultation with the HVTN 128 PSRT is required prior to subsequent infusion following any hypersensitivity reaction associated with study product
- Investigator determination in consultation with Protocol Team leadership (eg, for repeated nonadherence to study staff instructions)

Participants discontinuing study product administration for reasons other than pregnancy and HIV infection should be counseled on the importance of continuing with the study and strongly encouraged to participate in follow-up visits and protocol-related procedures per the protocol for the remainder of the trial, unless medically contraindicated (see HVTN 128 SSP).

Participants who become pregnant during the study should be encouraged to participate in follow-up visits (see Section 9.13). Participants diagnosed with HIV infection during the study should be encouraged to participate in follow-up visits (see Section 9.14).

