### 9.10.1 Assessment of systemic and local symptoms

Systemic symptoms to be assessed as Solicited AEs in this trial include increased body temperature, malaise and/or fatigue, myalgia, headache, chills, arthralgia, nausea, urticaria, non-exertional dyspnea, non-exertional tachycardia (assessed by HVTN CRS staff, not by the participant), generalized pruritus, facial flushing, and unexplained diaphoresis. Local symptoms include pain and/or tenderness at the infusion site. The daily maximum severity reached for each symptom during the assessment period is reported (see Ab MOP).

Body temperature is measured by oral or infrared thermometry. All temperatures must be measured by non-axillary thermometry. This includes temperatures taken in the clinic, as well as temperatures taken by participants during the Solicited AE period.

Temperature is reported in degrees Celsius. If temperature is measured in Fahrenheit, the conversion to Celsius should be documented in the participant's chart note. A measurement is taken once daily during the assessment period and should be repeated if participant is feeling feverish.

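### Table 11-1 footnote c exempts ten subjective solicited symptoms from prompt PSRT review at Grade 4 as well as Grade 3, although a related Grade 4 event permanently stops the participant's product

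*Protocol*

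**What the plan says.** Table 11-1 (Protocol 11.3) has a row for related adverse events (AEs) of Grade 4 or Grade 3. The site must email and submit forms at once. HVTN Core must notify the PSRT immediately, and the PSRT must review promptly and consider a pause. If that review is not finished within 72 hours of notification, not counting weekends and US federal holidays, the trial pauses automatically.

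Footnote c is attached to the event named in that row: "Does not include the following subjective Solicited AEs symptoms (infusion site pain and/or tenderness, fatigue/malaise, myalgia, arthralgia, chills, headache, non-exertional dyspnea, generalized pruritus". The list ends with facial flushing and unexplained diaphoresis. No grade is mentioned.

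Section 7.3.3 sets the rules for permanently stopping one participant's product. One trigger is "Any grade 4 local or systemic Solicited or Unsolicited AE that is subsequently considered to be related to study product". A separate trigger is "Any grade 3 clinical AE (exception: fever and subjective local and systemic symptoms"), again if considered related. The exception for subjective symptoms appears only in the Grade 3 rule.

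AEs outside Table 11-1 go to routine PSRT review (last sentence of 11.3). Under 11.4.2 this is weekly during the product administration phase.

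**The concern.** Stopping one participant and reviewing the whole trial are separate decisions, and their triggers need not match. At Grade 4, however, the order is reversed. A related Grade 3 fever does not stop dosing but reaches the PSRT immediately, because fever is not in footnote c. A related, non-serious Grade 4 event of a listed symptom stops dosing permanently but carries no such notice.

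What is at stake is early notice to the group that decides whether the other participants keep receiving infusions. Several listed symptoms bear on that decision. Section 4.8 names fatigue, chills, headache, dyspnea, pruritus and flushing among the signs of infusion reaction or cytokine release syndrome, and joint pains as a sign of serum sickness.

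**Working it through.** **1. Symptoms affected.** Section 9.10.1 begins "Systemic symptoms to be assessed as Solicited AEs in this trial include increased body temperature, malaise and/or fatigue, myalgia, headache, chills, arthralgia, nausea, urticaria" and in all lists 13 systemic symptoms plus one local symptom (infusion-site pain and/or tenderness): 13 + 1 = 14. Footnote c names 10 of them. The other 14 − 10 = 4 (increased body temperature, nausea, urticaria, non-exertional tachycardia) stay under prompt review at both grades.

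**2. The two rules side by side, for related, non-serious events.**

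| Event | Individual dosing (7.3.3) | PSRT route (Table 11-1) |
|---|---|---|
| Listed symptom, Grade 3 | not stopped (exception) | routine weekly review |
| Listed symptom, Grade 4 | stopped permanently | routine weekly review |
| Fever, Grade 3 | not stopped (exception) | immediate notice, prompt review |
| Fever, Grade 4 | stopped permanently | immediate notice, prompt review |

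Only the second row pairs a permanent stop with routine review. Related serious adverse events (SAEs) have their own rows in Table 11-1 without footnote c, so they are covered whatever the symptom. Both Table 11-1 and 7.3.3 list Grade 4 AEs separately from SAEs, so the protocol itself recognises a non-serious Grade 4 event.

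**3. Other routes to the PSRT before the weekly review.**

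- Section 2.5 states that "Safety is monitored daily by HVTN clinical staff and routinely by the HVTN 128 Protocol Safety Review Team". The daily task defined in 11.1.4 is "Daily monitoring of clinical data for events that meet the safety pause and HVTN 128 PSRT AE review criteria"; 11.4.1 adds events needing expedited reporting. An exempted non-serious event meets none of these criteria.
- Safety forms are due by the end of the next business day (11.2.1), but they go to the data center.
- Section 11.2.2: "Sites are expected to notify HVTN clinical safety staff of any serious safety concern requiring their attention". This rests on site judgement, goes to clinical safety staff and refers back to Table 11-1.
- Section 11.3 lets the PSRT suspend dosing for other concerns, but the PSRT must already know of the event.
- Section 7.3.3: "Consultation with the HVTN 128 PSRT is required prior to subsequent infusion following any hypersensitivity reaction associated with study product". This covers hypersensitivity only and is due before the participant's next infusion, with infusions 16 weeks apart.

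Mandatory routes found: none.

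**4. Size per event.** The plan gives no figure to reproduce. The assumptions are even accrual over the planned 5 months, events uniform between weekly reviews, and a prompt review that takes L days.

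- 5 months = 21.74 weeks. Infusions to the 23 other participants: 23 / 21.74 = 1.058 per week.
- Infusion rounds start at weeks 0, 16 and 32, and each spreads over 21.74 weeks. Two rounds therefore overlap in about weeks 16–22 and 32–38, when the rate is 2 × 1.058 = 2.116 per week.
- The wait W is uniform on 0 to 7 days, with mean 3.5 days. Mean days gained = E[max(0, W − L)] = (7 − L)² / 14.
- Infusions at stake = (days gained / 7) × weekly rate.

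| Prompt review takes | Mean days gained | Infusions, one round | Infusions, two rounds |
|---|---|---|---|
| L = 0 (immediate) | 49/14 = 3.50 | 0.53 | 1.06 |
| L = 3 (full 72 hours) | 16/14 = 1.14 | 0.17 | 0.35 |
| L = 5 (72 hours plus a weekend) | 4/14 = 0.29 | 0.04 | 0.09 |

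Extreme case (7-day wait, immediate review, overlapping rounds): 7/7 × 2.116 = 2.1 infusions. These count as avoided only if the review would have led to a pause.

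**The case against.** The best counter-argument is that the affected set may be empty. The event must be Grade 4, related, a listed symptom and non-serious. The grading table is not among the documents, and the one Grade 4 definition the protocol gives (infusion-site erythema and induration, 11.2.2) refers to potentially life-threatening consequences. Many such events might qualify as SAEs, and a related Grade 4 SAE pauses the trial at once. Severe dyspnea, pruritus or flushing might also be handled as a monoclonal antibody reaction under the study-specific procedures, which are not available here and could contain a faster route. This stands. It limits what can be said about frequency but does not change what the footnote says.

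Early notice is also likely in practice. The clinical safety specialist and the Core medical monitor sit on the PSRT (11.1.1), forms arrive by the next business day, and a site would ordinarily telephone about a Grade 4 reaction that ends dosing. This stands as a likelihood, but no text obliges anyone to tell the PSRT before the weekly review.

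Finally, the exemption looks deliberate: a trial-level trigger may reasonably leave out self-reported symptoms and keep measurable ones such as fever. That is a sound reason at Grade 3. At Grade 4 the protocol already treats the same report as sufficient to end dosing, and it gives no reason for withholding prompt review.

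**Conclusion.** The gap is real on the text. For 10 of 14 solicited symptoms, a related, non-serious Grade 4 event stops product permanently but has no assured route to the PSRT before the weekly review, and the 72-hour limit does not apply.

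The practical effect is probably small. The number of events cannot be estimated from the documents. Related AEs in VRC 605 peaked at Grade 2 (Protocol 4.8), so it may be near zero. That reassurance is incomplete, because repeat IV dosing in VRC 605 and HVTN 127/HPTN 087 reaches 20 mg/kg (4.7.1, Table 4-4) and this trial repeats 30 mg/kg. Under the accrual and timing assumptions above, usually fewer than one infusion to another participant is at stake per event. The main gain is assured earlier notice. No endpoint or analysis is affected. The change is worth making because it is cheap and concerns participant safety.

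**What to change.** Limit footnote c to Grade 3, for example:

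> Grade 3 events of these subjective solicited symptoms are excluded: [same ten symptoms]. Related Grade 4 events of these symptoms are not excluded.

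Leave 7.3.3, the Grade 3 exemption and the handling of fever as they are. A clarification memo or letter of amendment is enough, and no procedure or data collection is added.

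The cost is an occasional extra prompt PSRT review. If one overran 72 hours, the automatic pause would hold enrollment and dosing, and an infusion whose window then passed could not be given (7.3.2). If Grade 4 events are as rare as expected, this cost is equally rare.
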